- 2% of control group households will receive WRAP despite being allocated to the 'do not receive intervention' trial arm. This is based on trial arm non-compliance from previous children's social care RCT experience.
- 95% of intervention group receive intervention. This is estimated to be high, given that all households have expressed interest in the intervention.
- Upon administration of the endline survey, 5% of carers are untraceable. This is based on previous children's social care RCT experience.
- By the point of the endline survey, 2% of households withdraw consent. This is based on previous children's social care RCT experience.
- For the primary outcome, 5% have implausible or missing values. We anticipate this being low, as we will primarily rely on an online survey for our primary outcome with set response options.
- 20% of carers do not respond to the endline survey. We anticipate that this will be low due to the use of an incentive voucher, social worker engagement in advance of survey distribution, and a schedule of reminder text messages.

Figure 2. Consort diagram showing participants' journey through the pilot RCT of Barnardo's WRAP programme

To randomise we will set up a system where local authorities provide to Coram by email a unique family ID for each family expressing interest (consenting to participate in the

programme and study). Randomisation will be stratified by local authority. This will include fields to enable us to check whether local authorities have applied the eligibility criteria correctly, before we undertake randomisations (box 1).

We anticipate randomising around 178 households using a securely stored spreadsheet pre-populated with randomisation outcomes, and return the outcomes back to local authorities and Barnardo's within 24 hours. We will do this for the stock of families in March 2023, and then on demand as needed for the in-flow of newly eligible families thereafter until early 2024.

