4. We will work with Barnardo's to explore mechanisms for reminding participants of the endline survey, including social media, via fostering social workers, and at the Keeping Connected groups.
5. We will check whether contact details for participants are up-to-date with local authority records.

In order to minimise data storage and use the most up-to-date contact details, we will obtain contact details for all randomised carers from the Barnardo's Expression of Interest form.

Table 3. Milestones for outcome measure collection

Task	Date
Referrals of families sent by Barnardo's to Coram	March-April 2023
Eligible referred families randomised by Coram, then randomisation outcomes shared with local authorities and Barnardo's	March – April 2023
Coram emails/posts baseline survey to carers (with prompt text message, if mobile phone number available)	March – April 2023
Coram randomises eligible referred families, then emails/posts baseline surveys to carers (with prompt text message, if possible)	March 2023 – March 2024
Coram sends endline survey by email/post to carers (with prompt text message, if mobile phone number available)	1 st July 2024
Coram requests administrative data from local authorities	1 st July 2024
Coram sends reminder email/text message/post to non-respondent carers	July 2024
Deadline for local authorities to send Coram administrative data request Deadline for carers to complete endline survey	31 st July 2024

The online baseline and endline surveys are hosted on Smart Survey. The prompt text message will read:

'Hi, we're Coram. You may remember agreeing to take part in our study of families in Hull and Lincolnshire. Today we emailed you a survey about your experiences as a carer: [link]. Please complete by 30th April. We will send you a £10 voucher if you complete this survey, and we will also send you another £10 voucher if you complete an additional survey in July 2024.'

The reminder text for the endline survey will read:

'Last chance to have your say! We have emailed you a survey about your experiences as a carer. Your response will help Barnardo's and local authorities to offer the best possible wellbeing support to the fostering community. We will send you a £10 voucher if you complete this survey by 31st July. The link to the survey is [link]'

We will also consider including an additional prize draw in a reminder text, dependent on the response rate.

Type	Outcome	Outcome measure	Collected from	Baseline	Endline

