Under no circumstances will we break confidentiality in respect of answers to our online survey of carers. We have been advised that foster carers may be reluctant to honestly answer our questions about their wellbeing if there is a possibility the answers may be shared with their social worker or the local authority.

Participants will be anonymous in all outputs. We will not include any identifiable data, such as names. We will explore with advisors how best to report on the characteristics of interviewees (such as whether to specify their ethnic group), taking into consideration the small population group in only three local authorities. Anonymity will be explained clearly in information sheets to all participants. In interviews, the researcher will explain anonymity at the start and will check that the participant understands before proceeding with the interview. We will seek to interview no more than one family member per family, to help us maintain the confidentiality of stories we hear about how WRAP works within families.

Fieldwork with professionals

We will offer to interview professionals at a time which suits them, which may be a lunch break or before or after the working day. However, in at least some cases we are likely to take up the time of local authority professionals which could be used instead to provide services to children and young people. Accordingly, we have designed a survey and a topic guide to gather the minimum amount of data required to answer our research questions. We will test the draft questionnaire to ensure it takes under 10 minutes to complete, to lessen time as a barrier to participation. We will be flexible and offer to interview staff at the most convenient time for them to minimise disruption to services. Similarly, we will allow a whole month for staff to respond to the online survey.

The staff we approach may feel pressure to consent to take part in our evaluation or to give a positive account of progress in implementing WRAP. While we will encourage staff to take part in our survey and interviews, we will make clear (in information sheets and on the survey front page and/or invitation emails) that participation is voluntary, and answers will be treated confidentiality, and they will not be identifiable in any reporting. We will make clear

that we are interested in their personal views and experiences, and ensure privacy by checking before interviews that interviewees are in a suitable private location.

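### The scripted endline reminder names Barnardo's and the local authorities, does not identify Coram and omits the confidentiality assurance that the protocol treats as important for candid wellbeing answers

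*Protocol*

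**What the plan says.** The Outcome measures section gives the endline reminder word for word. After saying that a survey has been emailed, it tells carers that their response will help Barnardo's "and local authorities to offer the best possible wellbeing support to the fostering community", then mentions the voucher, the deadline and the link. The sender is only an unnamed 'we'. Table 3 shows who sends it and to whom: "Coram sends reminder email/text message/post to non-respondent carers". No restriction by arm is stated.

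Item 4 of the plans to raise response says the evaluator will explore with Barnardo's further ways of reminding participants, "including social media, via fostering social workers, and at the Keeping Connected groups". Among the CONSORT assumptions under Randomisation, one of the three reasons given for expecting low endline non-response is "social worker engagement in advance of survey distribution".

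Under Compliance, the Confidentiality and anonymity section reports advice that "foster carers may be reluctant to honestly answer our questions about their wellbeing" should their replies be able to reach a social worker or the authority. In response, it promises without exception to keep carer survey answers confidential.

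**The concern.** The primary outcome is WEMWBS, which carers complete knowing which arm they are in. The same survey carries perceived peer support, the carer-rated child checklists and SCORE-15. Answers of this kind can depend on who the respondent thinks is asking and who benefits.

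The only organisations named in the reminder are the body that delivers the intervention and the authorities that oversee the carers. One of these, the local authority, is a party that the protocol's own advice warns about. The reassurance adopted in reply to that advice is absent at this point of contact. The survey is also not anonymous: it asks for date of birth, initials, mobile number and email address so that answers can be matched to local authority records. A carer therefore has some reason to wonder who will see them.

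Two things are at stake: less candid answers among those who reply after the reminder, and possibly a different reaction in each arm, because one arm has been offered Barnardo's programme and the other asked for it and was allocated to usual support.

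**Working it through.** No arithmetic applies. The protocol gives no figure for a candour or demand effect, nor for the share of replies that follow the reminder. The check is a comparison of passages.

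1. **Parties named.** The reminder names Barnardo's and local authorities. The advice on candour names the social worker and the local authority. The overlap is the local authority alone. The point about Barnardo's rests on its role as deliverer, not on that advice.

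2. **What the reminder implies.** It says a response helps these bodies. It does not say they will see individual answers. The Confidentiality and anonymity section rules out disclosure of carer survey answers and restricts data access to Coram's evaluation team. What the protocol will do is therefore consistent; what remains is how the message may be read.

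3. **Where the assurance appears.** The Consent section says the front page of the survey will state that taking part is voluntary. It mentions no confidentiality statement there. Information sheets and a privacy notice are planned, but their text is not in the protocol, so whether they cover this cannot be judged.

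4. **Sender.** The scripted baseline prompt opens by identifying Coram and names neither Barnardo's nor the authorities. The endline reminder does the reverse.

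5. **Audience.** The survey goes to all carers in the trial, including kinship carers. The reminder speaks only of the fostering community.

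6. **Routes.** The scripted text goes to non-respondents in both arms. The social-worker route is only to be explored, although social-worker engagement already supports the response assumption, and Table 7 lists getting the message out to social workers as a mitigation for poor response. Keeping Connected groups follow the Level 1 WRAP groups, so a reminder given there would mainly reach the intervention arm. That could raise response in one arm only. Under Treatment of missing data, an association between missingness and arm switches the analysis from listwise deletion to last observation carried forward.

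7. **Direction.** Guardedness towards the authority could occur in both arms and, if equal, would largely cancel in the difference. Courtesy towards the deliverer would raise intervention-arm scores. Disengagement among controls could act either way: if controls with poor wellbeing stop replying, the observed control mean rises and the estimate moves against the intervention. The net sign is not determined.

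**The case against.** The strongest reply is that the protocol has already dealt with candour: confidentiality is unconditional, access is restricted, and carers receive information sheets and give consent at the start of the survey. Leaving the assurance out of one text message does not leave it out of the trial. Nor is Barnardo's involvement news to anyone, since it sends the invitations, runs the information sessions and collects the expressions of interest in both arms before randomisation. All of this stands, and it keeps the point small. It does not explain why the one fixed text should foreground these bodies and omit an assurance that costs one sentence.

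Stronger readings are tempting but not supported:

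- A reader might infer that carers do answer less honestly, or that the advice covers Barnardo's. The advice is conditional, says only that carers may be reluctant, and does not name Barnardo's.
- A reader might infer that the framing changes between survey waves. The comparison is between a baseline launch prompt and a last-chance reminder. An endline prompt is also scheduled, and no separate wording is given for it.
- A reader might infer a bias towards benefit and try to size it. For example, if 30% of replies followed the reminder and it shifted intervention-arm scores by 0.1 to 0.2 SD, the result would be 0.30 × 0.1 = 0.03 to 0.30 × 0.2 = 0.06 SD. Neither input has a source, and a zero shift or an equal shift in both arms is just as compatible with the documents.
- A reader might conclude that social workers should have no part in promoting the survey. That trades against response: the protocol's own figures put the MDES at 0.37 as planned and 0.40 if endline response falls to 65%. The documents do not show that the trade is worth making.

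**Conclusion.** The point holds as a modest, cheaply removed weakness in a fixed text. The reminder associates the wellbeing answers with the deliverer and the local authorities, does not say who is asking, and omits the assurance that the protocol elsewhere treats as mattering for honest replies. Because answers will not in fact be shared, this is a risk of perception and demand effects, not a conflict between sections. Its size and direction cannot be derived from the documents. The conclusion assumes only that some carers read the reminder before answering and that its wording can affect how they answer or whether they do. The omission of kinship carers is a plain wording slip.

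**What to change.** Replace the sentence on Barnardo's and local authorities with neutral wording from Coram, identical in both arms. For example: *This is Coram, the evaluator. We have emailed you a survey about your experiences as a foster or kinship carer. Your individual survey answers will not be shared with Barnardo's, your local authority or your social worker.* The voucher, deadline and link stay as they are.

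The text should not claim that answers go only to Coram. The Data protection section makes the funder a joint data controller and provides for a non-identifiable archive in the Office for National Statistics Secure Research Service, so that claim would be inaccurate.

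Send individual reminders from Coram by text, email and post. If social workers are involved, limit them to passing on the same message to carers in both arms. Drop Keeping Connected groups as a reminder route.

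The cost is an edit to one message and a narrower item 4 in the response plans. The downside is possibly slightly fewer late responses.

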Families who express an interest in taking part in the WRAP programme and its evaluation will be randomised to either a referral, or usual support for mental health and wellbeing, which includes providing information about existing services (50:50 split).

Randomisation will be at the family level. This means all household members in the intervention group will be referred. Barnardo’s aims to reach as many of the members of each target family as wish to take part. We believe this choice of unit will help address ethical and logistical concerns around randomisation (such as sibling dynamics). Having taken advice on terminology from advisors, we will avoid the use of ‘intervention group’ and ‘control group’ in communications with families.

We have outlined participants’ journey through the trial in the CONSORT diagram in Figure 2. This is based on the sample of participants available across the three local authorities. Foster families are more numerous than kinship families and will be prioritised by Barnardo’s, so our numbers below cover foster families and represent minima. We have included a separate CONSORT diagram with our estimation of kinship households in Annex 1, but do not want to rely on this given the lack of available data on the number of kinship carers. We have built the following assumptions into our estimations:

- 3% of households will be ineligible on the basis that there is at least one child in the household with an urgent or emergency mental health referral. This is an estimation based on the proportion of under-18s with an emergency referral, and an elevated level of mental health need in foster children⁷.

⁵ Rubin, D. M., O’Reilly, A. L. R., Luan, X., and Localio, R. (2007) ‘The Impact of Placement Stability on Behavioral Well-being for Children in Foster Care,’ *Paediatrics*, 119(2): 336-344.

⁶ Adams, E., Hassett, A. R., and Lumsden, V. (2018) ‘What do we know about the impact of stress on foster carers and contributing factors?’ *Adoption & Fostering*, 42(4): 338-353.

[figure not shown]
⁷Looked-after children and young people, NICE guideline (2021): www.nice.org.uk/guidance/ng205/chapter/Context

- 55% of invited households attend info session. This is a conservative estimate based on engagement experience of previous interventions in foster communities, i.e. foster carers being busy, having many commitments etc.

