We can expect that some children and young people will move to a randomised household during the observation period of the study, and that a proportion of these will move to a household randomised to a different trial arm. The Children's Commissioner (2020) found that, among children in care on 31 March 2019, most children (68%) had remained in their placement throughout the previous year, but 32% experienced one or more placement moves, 10% had experienced two or more placement moves, and 4.1% had experienced three or more. Teenagers and older children had the highest rates of placement instability. We have planned our administrative data returns to capture child and family ID codes, in order to trace the movement of children between households. We will report on the proportion of children that move between randomised households, in order to estimate the degree of trial arm 'contamination' in the current study and to predict this for a future full-scale RCT. We will also explore this in a compliance analysis (see Analysis plan).

Participants

The intervention and trial takes an inclusive approach to recruitment within households. The sample will therefore be made up of:

- Foster carers
- Kinship carers
- Foster children
- Kinship children
- Birth children, including children by blood, marriage, or legal adoption
- Other adults and children in fostering and kinship households, such as relatives and partners

Social workers also form part of fostering and kinship communities. Barnardo's will deliver services to FSWs as part of this programme, but social workers will not be randomised. Barnardo's have invited all FSWs in the three local authorities to take part in the WRAP intervention ahead of the trial, to aid programme buy-in and referrals.

Three local authorities volunteered to take part in the trial: Hull City Council; North East Lincolnshire Council; and North Lincolnshire Council.

Table 1. Information about participating local authorities

Local authority	Region	Type	Ofsted rating
Kingston Upon Hull City Council	Yorkshire and the Humber	Unitary	Requires improvement to be good (2023)
North East Lincolnshire Council	Yorkshire and the Humber	Unitary	Inadequate (2021)
North Lincolnshire Council	Yorkshire and the Humber	Unitary	Outstanding (2022)

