Primary outcome	Carer wellbeing	Warwick Edinburgh Mental Wellbeing Scale (WEMWBS, Tennant et al. , 2007)	Carer via online survey	✓	✓
Secondary outcome(s)	Perceived peer support networks	'How many other local foster carers or kinship carers could you ask for help if you needed it?'	Carer via online survey	✓	✓
	Child mental health	Brief Assessment Checklists for Children and Adolescents (Tarren-Sweeney, 2013)	Foster carer or kinship carer, reporting on all children currently in the household via online survey	✓	✓
	Foster child mental health	Strengths and Difficulties Questionnaire (Goodman, 2001)	Various informants, may be foster carer, social worker or young person via administration data request	✓	✓

	Family relationships	SCORE-15 (Stratton et al. , 2010)	Foster carer or kinship carer via online survey	✓	✓
	Placement changes	Administrative data: number of placements, dates of placement changes, reasons for placement changes.	Local authority data request		✓
Exploratory outcome(s)	Foster carer turnover	Administrative data: foster carer turnover, reason for foster carer ceasing to be a foster carer.	Local authority data request		✓
	Service use/help seeking	Administrative data: referrals to CAMHS of foster children, dates of referrals, reasons for referrals (presenting issues).	Local authority data request		✓

For the online survey, we have consulted our advisors in finalising our choice of measures for primary data gathering directly from families. Each foster carer completing the survey will be sent a £10 incentive voucher, and we have timed the survey at around 15 minutes to complete. On the final page of the survey, participants will be asked which voucher they want to receive from a choice of two options (we anticipate using Amazon and Love2Shop). Measures will be completed by carers, but the survey will ask carers to answer questions about themselves, their foster children, their kinship children, and their birth children. The online survey includes:

- Questions referring to **foster and kinship carer demographic** information. This includes date of birth, initials, mobile phone number, and email address. We will not ask any further details, as we want to minimise burden and intend to match this data with local authority data using these fields.

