- Questions referring to **demographics of children** currently in the household. This includes birth, foster, kinship, adoptive, and step children. We will request the child's date of birth and initials to allow data matching.
- A measure of **peer support**: the number of other local foster carers or kinship carers the foster carer could ask for help. The survey will prompt for a numerical answer, and the question will read 'How many other local foster carers or kinship carers could you ask for help if you needed it?'
- A measure of **carer self-reported wellbeing**: the Warwick Edinburgh Mental Wellbeing questionnaire (Tennant *et al.*, 2007). This is a 14-item self-report scale of positively worded wellbeing items and has been validated for use with individuals aged 13 years and above. The psychometric properties of the measure are well-

established, and it has demonstrated sensitivity to change (Collins *et al.*, 2012¹⁷; Maheswaran *et al.*, 2012¹⁸).

- A measure of **carer-reported child wellbeing**: the Brief Assessment Checklist for Children and Adolescents (BAC-A; Tarren-Sweeney, 2013). The BAC-A is a 20-item caregiver-reported measure of mental health difficulties in children and adolescents aged 4-17 years. The measure was developed specifically for children and young people in foster, kinship, and residential care, and children who are adopted. We will ask for a BAC-C or BAC-A (dependent on child age) for every child in the household aged four and above. These outcome measures were developed for use with looked-after children and children with experience of trauma. From our consultations with foster carer advisors, we heard that foster carers see the use of equivalent measures for foster and non-foster children as a positive as foster children are not made to feel different. We have reviewed the items in the BAC-A and BAC-C and none of them seem inappropriate for non-foster children. We anticipate that non-foster children may score differently on these.
- A measure of **carer self-reported family relationships**: the SCORE-15 (Stratton *et al.*, 2010). The Systemic Clinical Outcome and Routine Evaluation-15 (SCORE-15) is a self-report measure of family processes and relationships. While the 15-item version is a relatively new measure, there is evidence to support its psychometric properties.¹⁹

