1. Has the foster carer ceased fostering? (yes, no)
2. Why has the foster carer ceased fostering? (resignation, uncontested termination of approval, contested termination of approval, other, unknown)
3. Other reason (if applicable)
4. Contributing factors (e.g. illness)

We will also seek data on referrals to Child and Adolescent Mental Health Services - **CAMHS referrals** - for foster children in the fostering household. From discussions with local authority data leads, it is likely that where this information is centrally stored, it will only be available for foster children in the household and not other children. This analysis will be exploratory only.

While not an outcome variable, we also intend to request data from Barnardo's on **engagement** with the intervention. This will include attendance at information sessions, the number of WRAP sessions attended and the dates of WRAP sessions. The intervention is designed to be self-sustaining, so we will also gather and match in data from Barnardo's on who leads the ongoing Keeping Connected groups. This will allow us to describe the delivery of the intervention in the final report and will be used in the compliance analysis.

Analysis plan

Does the intervention work?

Q1 Analysis

The trial will take an RCT design. The primary outcome will be collected at baseline (for most families, March 2023) and endline (for all families, July 2024). All outcomes will be analysed on an intention to treat basis in that all participants will be analysed according to the trial arm to which they were assigned, as opposed to the service they received.

Families are the unit of randomisation, but data will be analysed at the individual level e.g. individual foster child placement breakdown, individual foster carer turnover, and individual SDQ outcomes for foster children. We will need to account for clustering within our analysis. We may receive two responses from couples. In this case, we will use clustered standard errors to account for this.

We know from prior experience of analysing routinely collected Strengths and Difficulties scores for looked-after children that local authorities do not generally know or collect data on the version of the SDQ used and who completed it (carer, child, or social worker). We therefore anticipate it will be challenging to standardise scores on the SDQ by informant, but will do so if data allows.

Data cleaning

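### The endline BAC is taken on children living in the household at that date, so the comparison is of endline residents, not of the children in the families at randomisation

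*Protocol*

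**What the plan says.** - **Collection.** In the outcomes table of the Outcome measures section, the child mental health row has a foster or kinship carer "reporting on all children currently in the household via online survey", with baseline and endline both ticked. The description of the survey asks for a BAC-C or BAC-A "for every child in the household aged four and above".
- **Matching fields.** For children in the survey: "We will request the child's date of birth and initials to allow data matching". Annex 3 also lists names, IDs and dates of birth of foster and other children at randomisation.
- **Randomisation and analysis.** "Randomisation will be at the family level". Under Analysis plan: "Families are the unit of randomisation, but data will be analysed at the individual level", and on intention to treat, "all participants will be analysed according to the trial arm to which they were assigned". For the children's mental health outcome, Secondary outcomes analysis names linear regression and the children in the household, and nothing narrower.
- **Movement.** The Randomisation section expects children to move and cites a national source in which "32% experienced one or more placement moves" in a year. It plans to trace children by ID, report the proportion moving between randomised households, and explore this in the compliance analysis.
- **Timing.** Most baselines fall in March 2023, randomisation continues to March 2024, and the endline survey goes out in July 2024.

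**The concern.** Which children live in a household at endline is settled after randomisation, by whether placements held. The trial treats placement change as a secondary outcome and asks whether WRAP alters it. The BAC is then measured on a group that this same process has selected.

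Three kinds of child are affected:

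- A child who leaves for a home outside the trial has no endline BAC, because the survey goes only to trial carers.
- A child placed after randomisation has an endline BAC but was not in the family when it was allocated.
- A child who moves to another randomised household is reported by the new carer, and the protocol does not say to which arm that score belongs.

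If stability differs between arms, a BAC difference could appear or be hidden without any change in a child's mental health. Arrivals with little exposure would also pull a real effect towards zero. The SDQ (outcome 3b) is returned by child ID and so follows the original foster child. The two measures of one outcome could therefore describe different foster children.

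**Working it through.** **Is there a figure in the plan to reproduce?** Not for the BAC. The only precision figure is the minimum detectable effect for the carer primary outcome. With the Annex 2 inputs, the standard error is sqrt[0.4/(0.25×123.9) + 0.6×0.4/(0.25×123.9×1.9)] = 0.130, where 123.9 = 41.3×3. The multiplier t(0.975)+t(0.80) on 3×(41.3−2) = 117.9 degrees of freedom is 2.825, giving 0.368 against the stated 0.37. It concerns adults and says nothing about the BAC.

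**Does another provision already settle which children count?**

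- The intention-to-treat sentence fixes the arm, not the set of children.
- The movement reporting covers only moves between randomised households. It omits children who leave the trial's households altogether and children who arrive from outside.
- The Compliance section deals with session attendance and contains no step for movers.
- Treatment of missing data gives listwise deletion, or last observation carried forward if missingness differs by arm. Neither supplies a leaver's endline score, and a leaver counts as missing only if the set is defined at randomisation.

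**How many foster children might move?** With a constant rate and 68% staying per year, the share moved by m months is 1 − 0.68^(m/12).

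- m = 4 (randomised March 2024): 1 − 0.68^(4/12) = 0.121
- m = 16 (randomised March 2023): 1 − 0.68^(16/12) = 0.402

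The BAC also covers birth and kinship children. If only foster children move, the shares over foster plus birth children are:

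- On the target of 544 foster and 59 birth children (603): 66/603 = 11% to 219/603 = 36%.
- On 1.88 foster children per family (Exclusion criteria), 178×1.88 = 335 foster plus 59 birth (394): 40/394 = 10% to 135/394 = 34%.

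**Selection from leavers.** Assume scores and the propensity to move are jointly normal with correlation r, and a share s stays. The stayers' mean is then −r·φ(z)/Φ(z) with Φ(z) = s.

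- s = 0.60: ratio 0.644. s = 0.70: ratio 0.497. Difference 0.147.
- With 60% staying in control and 70% in intervention, r = 0.2, 0.4, 0.6 gives 0.029, 0.059, 0.088 SD, against WRAP because a higher BAC means more difficulties.

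A simpler check: if leavers score d SD worse than stayers and shares qC and qT leave, the spurious difference among stayers is (qC − qT)·d.

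- 40% v 30% leaving, d = 0.3 to 0.8: 0.03 to 0.08 SD
- 32% v 27%: 0.015 to 0.04 SD
- 32% v 32%: 0

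**Dilution from arrivals.** If a share a of endline children are arrivals with no effect at all, a true effect d becomes (1 − a)·d. For a = 0.12 this is 0.88d, and for a = 0.36 it is 0.64d. Partial exposure of arrivals gives less shrinkage.

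**The case against.** The strongest case against has four parts.

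1. **Estimand.** Families are randomised, and the evaluation question is the effect of referring a family on children in fostering and kinship households. Comparing children living in those households at endline is a recognisable household-level question. This stands in part. It rules out saying that randomised children have been replaced by non-randomised ones, since no child was randomised individually. It does not remove the dependence on a post-randomisation event that is itself an outcome.
2. **Arrivals may be exposed.** All household members in the intervention arm are referred, with no statement that membership is frozen at randomisation. Delivery runs to June 2024, and carers are trained so that they can better support the family. This stands. A reader might infer that 40% of endline foster-child reports come from children who were never referred and that an effect falls to 0.6d. That needs every leaver replaced and zero effect on every arrival, and the protocol supports neither.
3. **The movement rate is an upper-end figure.** It is national, families on the verge of breakdown are excluded, many families enter after March 2023, and moves concentrate in older children. This stands.
4. **It belongs in the SAP.** An analysis set for one secondary outcome is often defined there, and arrivals can be separated using data already collected. This stands for arrivals only as far as feasibility goes: the protocol as written pools them. It does not hold for leavers, because no later plan can recover a BAC that was never requested.

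**Conclusion.** The point holds in a limited form. As written, the BAC contrast compares children resident at endline, and the protocol's provisions on intention to treat, movement, compliance and missing data do not change that.

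A reader might go further and infer that the BAC result will be biased. The documents do not support this. Selection bias is zero if leaving is equal and alike in both arms. The 0.03 to 0.09 SD rests on an assumed 10-point difference in staying and an assumed r of 0.2 to 0.6, neither of which has a source in the protocol. The 12% to 40% movement range rests on a national rate held constant and applies to foster children only.

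This is a worthwhile, inexpensive improvement to one of two measures of one secondary outcome in a pilot. It does not touch the primary outcome.

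**What to change.** 1. Define the main BAC analysis set as children listed in the household at randomisation, matched to endline by date of birth and initials.
2. Analyse each child by the arm of their family at randomisation, including any child who has since moved to another randomised household.
3. Show later arrivals separately, as a sensitivity analysis.
4. Report the number and share of leavers and arrivals by arm, and treat leavers as missing outcome data.
5. State that the BAC result is conditional on staying, and use the child-ID-linked SDQ as a partial check. It covers foster children only.

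**Cost.** This is a change of wording, since the matching fields are already in the survey and in Annex 3. The main analysis will contain fewer BAC reports. The Participants section says birth-child data are not systematically held by the local authorities, so the randomisation list for those children should be checked for completeness. The change takes arrivals out of the main contrast. Selection from leavers is disclosed and partly checked, but not removed.
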